## 8.2 Calculation of Key Measures

The following efficacy assessments will be used to assess subjects' disease activity and severity during the study. Outcomes are reported via an eCOA tool at various times throughout the study as described in the protocol Schedule of Activities. At study visits, assessments by the investigator or subjects and results/responses will be reported directly into the eCOA tool at the time of the visit. The tool will open assessments in a sequential manner, meaning that the full assessment is to be completed prior to moving forward to the next assessment. This limits the possibility of partially missing data. Also, as investigators/subjects are prompted to enter data for each assessment for the visit, the possibility of a full assessment being missing is also negated.

Scoring of assessments where validated algorithms are not required will be derived in SAS datasets.

Scoring of assessments where validated scoring tools are required, licenses for these tools will be purchased and used for scoring prior to incorporating into the SAS datasets.

### 8.2.1 Investigator-Administered Assessments

Assessments will be performed by a qualified physician or dermatologist or trained designee who is experienced in the assessment of psoriasis patients. To limit variability, every effort will be made so that the same individual conducts the assessment at all subsequent visits.

#### 8.2.1.1 static Physician's Global assessment (sPGA)

The sPGA is a 5-point scale of an average assessment of all psoriatic lesions based on erythema, scale, and induration. The sPGA measure determines psoriasis severity at a single point in time (without taking into account the baseline disease condition) as clear (0), almost clear (1), mild (2), moderate (3), or severe (4). A higher score equates to higher severity of disease.

The individual scores at each visit for erythema (E), induration (I) and scaling (S) will be captured via the eCOA system. Scores will range from 0 to 4. A total score will also be computed based on the average of the 3 characteristic scores.

$$\text{Total average score} = \frac{E + I + S}{3}$$

The total average score will be calculated in the eCOA system. The average score will be rounded to the nearest whole number. For example, if the total average score is ≤1.49 the score will be rounded to 1. If

Sponsor: Bristol-Myers Squibb

Protocol no: IM011046

the score is  $\geq 1.5$  the score will be rounded to 2. The primary endpoint is derived from the total average score.

sPGA 0 is derived as the binary indicator for sPGA from the calculation above equal to 0 or not;

sPGA 0/1 is derived as the binary indicator for sPGA from the calculation above equal is less than 2 or not;

All individual scores and total average score assessed at each week throughout the study will be transferred to PRA for analysis. The endpoint derivations will be performed in the analysis datasets.

#### 8.2.1.2 Psoriasis Area and Severity Index (PASI)

The PASI is a measure of the average redness, thickness, and scaliness of psoriatic skin lesions (each graded on a 0–4 scale; 0 = none to 4 = very severe), weighted by the area of involvement (head, arms, trunk to groin, and legs to top of buttocks). The PASI produces a numeric score that can range from 0 to 72, with higher PASI scores denoting more severe disease activity. The PASI includes multiple subscores and a final total score that will be provided by the eCOA system. Individual plaque characteristic rating scores are provided for each body region as well as the weighted score. Additionally, the degree of involvement of each body region is assessed and that score is multiplied by the weighted plaque characteristic score for a final score for each body region. The total PASI score is a sum of the 4 body regions: Head, Upper Extremities, Trunk and Lower Extremities.

The PASI Total score will be used to assess response to treatment. The percent change from baseline will be calculated at each visit. The PASI 75 endpoint is the proportion of subjects who experience at least a 75% improvement in PASI score as compared with the baseline value.

$$1 = If \left( \frac{\text{Baseline PASI} - \text{Visit PASI}}{\text{Baseline PASI}} \right) \times 100 \geq 75 \text{ then subject is a PASI 75 responder}$$

0 = otherwise

The PASI 50, PASI 90, and PASI 100 are defined similarly. The endpoint derivations will be performed in the analysis datasets.

#### 8.2.1.3 Body Surface Area (BSA)

Measurement of psoriasis BSA involvement is estimated using the handprint method with the size of a subject's handprint (including fingers and thumb) representing 1% of BSA involved. The total BSA = 100% with breakdown by body region as follows:

- Head and neck = 10% (10 handprints),
- Upper extremities = 20% (20 handprints),
- Trunk including axillae and groin = 30% (30 handprints),
- Lower extremities including buttocks = 40% (40 handprints).

The Total BSA is the sum of each body region and is assessed at each visit and recorded in the eCOA system.

The product of BSA and sPGA will be calculated. At baseline, baseline BSA will be multiplied by baseline sPGA score. The derivation will be performed at each subsequent visit.

#### 8.2.1.4 scalp specific Physician's Global Assessment (ss-PGA)

[figure not shown]
The scalp specific assessment will only be performed in subjects with scalp involvement. If there is evidence of scalp involvement, scalp lesions are evaluated in terms of clinical signs of redness, thickness, and scaliness and scored on the following 5-point ss-PGA scale:

0 = absence of disease, 1 = very mild disease, 2 = mild disease, 3 = moderate disease, 4 = severe disease.

Sponsor: Bristol-Myers Squibb

Protocol no: IM011046

The ss-PGA is assessed at each visit throughout the study in subjects that have evidence of scalp psoriasis at baseline. The score will be collected in the eCOA system.

[figure not shown]

#### 8.2.1.6 Physician's Global Assessment-Fingernails (PGA-F)

In this assessment, fingernail psoriasis is evaluated. The PGA-F will be performed at baseline. If a subject shows evidence of psoriatic fingernail involvement, the assessment will be performed at each subsequent visit to assess severity and improvement over time. Only subjects with PGA-F at baseline will be assessed throughout the study. The overall condition of the fingernails is rated on a 5-point scale:

0 = clear, 1 = minimal, 2 = mild, 3 = moderate, and 4 = severe

The rating score will be collected in the eCOA system.

Sponsor: Bristol-Myers Squibb

[figure not shown]
Protocol no: IM011046

### 8.2.1.8 Palmoplantar PGA (pp-PGA)

This measure will be used for subjects with palmoplantar (finger and toe surfaces) involvement at baseline. Only subjects with baseline palmoplantar involvement will continue to have these assessments at each subsequent visit throughout the study. The pp-PGA uses a 5-point (0-4) overall severity scale:

0 = clear; 1 = almost clear; 2 = mild; 3 = moderate; and 4 = severe.

Scores are collected at each visit and entered in the eCOA system.

## 8.2.2 Subject-Reported Assessments

### 8.2.2.1 Psoriasis Symptoms and Signs Diary (PSSD)

The PSSD is an 11-item subject-reported instrument that assesses severity of symptoms and subject-observed signs commonly associated in plaque psoriasis. It has been shown to be reliable and valid in measuring symptoms and signs of subjects with moderate-to-severe plaque psoriasis in the clinic and has strong psychometric properties in assessing treatment effects in clinical trials. The PSSD assesses severity of 5 symptoms (itch, pain, stinging, burning, skin tightness) and 6 subject-observed signs (skin dryness, cracking, scaling, shedding or flaking, redness, bleeding) using 0–10 numerical ratings. The severity of each item is rated on an 11-point numeric rating scale ranging from 0 (absent) to 10 (worst imaginable).

The following questions in the instrument are included in the symptom score: Q1, Q4, Q9, Q10, Q11

The following questions in the instrument are included in the sign score: Q2, Q3, Q5, Q6, Q7, Q8

Two versions of the PSSD were developed, one with a 24-hour recall period (PSSD-24h) and one with a 7-day recall period. The PSSD-24h will be administered daily in this trial to avoid recall bias with a longer recall period. Individual scores to each question are collected daily in the PSSD. For visit PSSD scoring, the daily scores (with 24-h recall periods) over the prior 7 day will be used and the average score to each of the 11 questions will be used as the score at that visit. In case missing data arise during the 7 days prior to the visit, daily scores of at least 4 days out of the 7 can be used. If >3 scores are missing, the average score will be missing. Baseline PSSD score is calculated based on the daily diary collected data during the screening period. Baseline for each PSSD question will be calculated as the average value over the 7 days

Sponsor: Bristol-Myers Squibb

[figure not shown]
Protocol no: IM011046

prior to the randomization visit. In the event of missing values in the 7 days prior to the randomization visit, daily scores from at least 4 days out of the 7 days can be used to calculate the average score. If > 3 daily scores in the last 7 days are missing for a particular question, then the baseline value for that question will be missing. If any questions are missing baseline after using the described rule, then the baseline value for the subscore using that question and the baseline value for the total score will be missing.

A symptom score will be derived by averaging the 5 questions included in the symptom score and multiplying by 10. To obtain a symptom score on a given day, responses to at least 2 of the 5 questions must be available. If 3 or more questions are missing, the symptom score is considered missing.

A sign score will be derived by averaging the 6 questions included in the sign score and multiplying by 10. Responses to at least 3 of the 6 questions must be available in order to obtain a sign score for a given day. If more than 3 questions are missing, the sign score is considered missing.

Both scores range from 0-100, where 0 representing the least severe symptom/sign and 100 the most severe. A total PSSD score with range 0-100 will be derived from taking the average of the symptom and sign scores.

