**Table 1: Screening Procedural Outline (IM011046)**

Procedure	Screening V1	Notes
TSH	X	If TSH above normal reference range, test free T4; if TSH below normal range, test free T4 & T3
hs-CRP	X	
Serology	X	Includes HCV antibody, HBsAg, HBsAb, HBcAb, HBV DNA, and HIV antibodies
TB Test	X	In accordance with QuantiFERON-TB Gold. (details described in Section 8.4.4).
Pregnancy Test (serum)	X	For WOCBP only
FSH	X	To confirm menopausal status (see APPENDIX 4)
Clinical Efficacy/Health Outcomes		
sPGA	X	
PASI	X	
BSA	X	
PASE Questionnaire	X	For subjects with peripheral joint complaints to screen for presence of psoriatic arthritis
PSSD	X	All consented subjects will be given a diary device at the Screening Visit and will begin recording psoriasis signs and symptoms on a daily basis in the diary device. Subjects who are not randomized will stop recording and return their diary device to the site. Subjects who are randomized will continue recording their psoriasis signs and symptoms on a daily basis in the diary device through Week 52.

BSA = body surface area; CBC = complete blood count; DNA = deoxyribonucleic acid; ECG = electrocardiogram; eC-SSRS = electronic Columbia-Suicide Severity Rating Scale; FSH = follicle-stimulating hormone; HBV = hepatitis B virus; HBcAb = hepatitis B core antibody; HBsAb = hepatitis B surface antibody; HBsAg = hepatitis B surface antigen; HCV = hepatitis C virus; HIV = human immunodeficiency virus; hs-CRP = high-sensitivity C-reactive protein; IRT = interactive response technology; PASE = psoriatic arthritis screening and evaluation; PASI = Psoriasis Area and Severity Index; PE = physical examination; PHQ-8 = eight-item Patient Health Questionnaire; PsA = psoriatic arthritis; PSSD = Psoriasis Symptoms and Signs Diary; SAE = serious adverse events; sPGA = static Physician Global Assessment; T3 = triiodothyronine; T4 = thyroxine; TB = tuberculosis TSH = thyroid-stimulating hormone; V = visit; WOCBP = women of childbearing potential

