# 8.0 Conventions

## 8.1 General Definitions

The following data definitions and handling conventions will be used for general analysis:

Term	Definition
Study Day	Study day is calculated as: assessment date – date of first dose + 1
Baseline	Unless otherwise stated, Baseline is defined as the measurement at the randomization visit (Week 0). If the measurement at the randomization visit is missing, then a prior measurement during the screening period may be used as baseline. Baseline assessments must be performed per protocol and standard of care assessments may not be used for baseline. Baseline for each PSSD question will be calculated as the average value over the 7 days prior to the randomization visit. In the event of missing values in the 7 days prior to the randomization visit, daily

Sponsor: Bristol-Myers Squibb  
Protocol no: IM011046

	scores from at least 4 days out of the 7 days can be used to calculate the average score. If > 3 daily scores in the last 7 days are missing for a particular question, then the baseline value for that question will be missing. If any questions are missing baseline after using the described rule, then the baseline value for the subscore using that question and the baseline value for the total score will be missing.
Change from Baseline	Change from baseline is defined as (value at post-baseline visit – value at baseline).
Change in the maximum post-baseline value or change in the worst post-baseline value	Change from baseline in the maximum post-baseline value is defined as highest observed value or grade post-baseline. The change is calculated using this value as the post-baseline value.  Change from baseline in the worst post-baseline value is defined as worst observed value post-baseline. The change is calculated using this value as the post-baseline value.
Concomitant and Prior Medication	Prior medications are defined as medications with a stop date prior to the first dose of study treatment. Concomitant medications are defined as any medications ongoing at the start of study treatment or with a start date on or after the first dose date.
End of Study (EOS) Date	The EOS date is the date recorded on the eCRF that a randomized subject either discontinued or completed the study. If the subject is lost to follow-up, the EOS date will be the date of the last visit assessment obtained.

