## 8.5 Day Ranges for Analysis Visits

Below are the day ranges for the analysis visit definitions. If more than one visit occurs within an analysis visit, then the visit that is closest to the target date should be used for analysis.

Period	Week	Target Day	Day Range
Baseline			Screening, 1
Period 1			
Week 1		8	2, 11
Week 2		15	12, 18
Week 4		29	19, 43
Week 8		57	44, 71
Week 12		85	72, 99
Week 16		113	100, 127 (or Week 16 drug dispense date)
Period 2			
Week 20		141	1 st day after Week 16 drug dispense date, 155

Sponsor: Bristol-Myers Squibb

Protocol no: IM011046

Period			
Week	Target Day	Day Range	
Week 24	169	156, 183 (or Week 24 drug dispense date)	
Period 3			
Week 28	197	1 st day after Week 24 drug dispense date, 211	
Week 32	225	212, 239	
Week 36	253	240, 267	
Week 40	281	268, 295	
Week 44	309	296, 323	
Week 48	337	324, 351	
Week 52	365	352, last visit date prior to Safety Follow-up	
Safety Follow-up	393	Safety Follow-up visit	

Sponsor: Bristol-Myers Squibb  
Protocol no: IM011046

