	pp-PGA 0/1 among subjects with a baseline pp-PGA $\geq 3$			
PSSD / Symptom Score (Sec 8.2.2.1)	PSSD/Symptom 0 among subjects with baseline PSSD/symptom score $\geq 1$	W16	BMS vs. PBO BMS vs. apremilast	CMH (Sec 6.1.2.1) CMH (Sec 6.1.2.1)
		Baseline->W16 over time	BMS vs. PBO	Binary GEE & CMH by Week (Sec 6.1.5.1)

Sponsor: Bristol-Myers Squibb  
Protocol no: IM011046

Assessment	Outcome Measure	Endpoint	Comparison	Analyses
DLQI (Sec 8.2.2.4)	DLQI 0/1 among subjects with a baseline DLQI score $\geq 2$	W16 Baseline->W16 over time	BMS vs. PBO BMS vs. PBO	CMH (Sec 6.1.2.1) Binary GEE & CMH by Week (Sec 6.1.5.1)

Sponsor: Bristol-Myers Squibb  
Protocol no: IM011046

Assessment	Outcome Measure	Endpoint	Comparison	Analyses
PASE (Sec 8.2.2.11)	PASE	Screening only		No Analysis

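### Week 1 PSSD scores can reuse baseline diary entries, because the 7-day look-back has no floor at first dose

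*SAP*

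**What the plan says.** - **Visit score.** SAP Section 8.2.2.1: "For visit PSSD scoring, the daily scores (with 24-h recall periods) over the prior 7 day will be used". If entries are missing, "daily scores of at least 4 days out of the 7 can be used".
- **Baseline.** SAP Section 8.1: "Baseline for each PSSD question will be calculated as the average value over the 7 days prior to the randomization visit". The same minimum of 4 entries applies.
- **Study day.** SAP Section 8.1 defines it as "assessment date – date of first dose + 1", so the first-dose date is Day 1 and the day before it is Day 0.
- **Week 1 timing.** Protocol Table 2 schedules the visit at Day 8 with a tolerance of 3 days either side, that is Days 5 to 11. SAP Section 8.5 assigns Days 2 to 11 to Week 1, with target Day 8.
- **Choice among visits.** SAP Section 8.5: "If more than one visit occurs within an analysis visit, then the visit that is closest to the target date should be used for analysis". These ranges select visits and do not map diary days.
- **Diary.** Protocol Table 1: "Subjects who are randomized will continue recording their psoriasis signs and symptoms on a daily basis in the diary device through Week 52".
- **Use.** For PSSD symptom score 0 versus placebo, from baseline to Week 16, SAP Appendix 2 lists "Binary GEE & CMH by Week (Sec 6.1.5.1"). Protocol Table 4 places PSSD change from baseline under the objective that runs through Week 16.

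**The concern.** The diary is daily and each entry looks back 24 hours, so a post-treatment week can be separated cleanly from the pre-treatment week. The scoring rule does not do this. It counts back 7 days from whatever date the clinic visit took place, and at Week 1 that count can reach past first dose into the days that make up the baseline mean.

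Two results suffer. In change from baseline, the shared entries sit in both terms and contribute no treatment effect. In PSSD symptom score 0, a mean of zero needs every averaged entry to be zero. One nonzero pre-dose entry in the window rules out a Week 1 response, whatever happened after dosing. How far the result is diluted depends on visit timing rather than on treatment.

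**Working it through.** The plan gives no figure to reproduce, so the check is a count of days.

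**Inputs.** Visit window of 7 days before the visit, and a minimum of 4 entries (SAP 8.2.2.1). Baseline window of 7 days before randomization (SAP 8.1). Week 1 visit on Days 5 to 11 (Protocol Table 2) or Days 2 to 11 (SAP 8.5). Assumption: first dose falls on the day of the randomization visit, so baseline covers Days −6 to 0.

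**Formula.** A visit on study Day v uses Days v−7 to v−1. Entries shared with baseline are those dated Day 0 or earlier: k = 8 − v for v = 2 to 8, and 0 after that.

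| Visit day | Look-back days | Shared with baseline | Accepted by |
|---|---|---|---|
| 2 | −5 to 1 | 6 of 7 (86%) | SAP only |
| 3 | −4 to 2 | 5 of 7 (71%) | SAP only |
| 4 | −3 to 3 | 4 of 7 (57%) | SAP only |
| 5 | −2 to 4 | 3 of 7 (43%) | both |
| 6 | −1 to 5 | 2 of 7 (29%) | both |
| 7 | 0 to 6 | 1 of 7 (14%) | both |
| 8 | 1 to 7 | 0 | both |
| 9 to 11 | 2–8 to 4–10 | 0 | both |

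**Dilution.** If the effect were constant from the Day 1 entry onwards (an assumption), the Week 1 mean would show 1 − k/7 of it: 6/7 = 86% at Day 7, 5/7 = 71% at Day 6, 4/7 = 57% at Day 5 and 1/7 = 14% at Day 2.

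**Incomplete diary.** If three post-baseline entries are missing, 4 entries remain and the score still counts. The baseline share is then 1/4 = 25% at Day 7, 2/4 = 50% at Day 6 and 3/4 = 75% at Day 5.

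**Later weeks.** At the earliest day that SAP 8.5 accepts, Week 2 (Day 12) uses Days 5 to 11, Week 4 (Day 19) uses Days 12 to 18, and Week 16 (Day 100) uses Days 93 to 99. None of these overlaps baseline.

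**Would simple truncation do?** Dropping entries dated Day 1 or earlier leaves v − 2 entries for a visit between Days 5 and 8. That is 3 at Day 5, below the minimum of 4, so the score would be missing. At Day 6 it leaves 4, with no room for a missed entry.

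**The case against.** The case against runs as follows. The overlap occurs in every arm and dilutes the contrast, so it does not favour the study drug. A visit on the nominal Day 8 shares nothing with baseline. A Day 2 visit counts only if no visit in the range lies closer to Day 8. PSSD symptom 0 at Week 1 is demanding anyway, because one nonzero entry on Days 2 to 7 rules it out just as surely. The only visible by-week PSSD analysis is the binary one. The visible ANCOVA is at Week 16, and the section to which Appendix 2 refers for the by-week method is not in the public text, so a window rule there cannot be excluded.

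All of this stands, and it keeps the point small. It does not remove it. Section 8.2.2.1 is where PSSD scoring is defined, its rule is visible, and following it gives the overlaps in the table.

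Two stronger readings are tempting, and the documents do not support them.

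- A reader might infer that a Week 1 score is mostly baseline data. With a complete diary, a visit inside the protocol window shares at most 3 of 7 entries; a majority needs a visit on Days 2 to 4. Counting the Day 1 entry as pre-dose would give 4 of 7 at Day 5, but that entry is not in the baseline. The documents also set no time of day for the diary, so how much of its recall precedes dosing is unknown.
- A reader might infer that a missed Week 16 visit throws away a complete diary week. The SAP says nothing about that case, and any visit on Days 100 to 127 supplies an anchor. SAP Section 6.6.1 says that all subjects still in the trial completed the Week 16 and Week 24 visits before COVID-19 restrictions. The documents show no such loss.

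**Conclusion.** The concern holds as a minor defect confined to Week 1. For visits within the protocol window, 1 to 3 of the 7 entries are reused at Days 7 to 5; for visits that only the SAP range accepts, 4 to 6 are. The direction is towards no effect in all arms. It touches the by-week PSSD symptom 0 comparison and any Week 1 display of PSSD change. The windows for Weeks 2 to 16 contain no baseline entry, so the Week 16 key secondary endpoints are not affected.

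The counts assume that dosing starts on the randomization day and that the look-back excludes the visit day. If it included the visit day, the overlap would be 2 entries at Day 5 and 5 at Day 2. The documents do not say how many subjects are seen before Day 8, so the average dilution across the trial cannot be calculated.

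**What to change.** Add two sentences to SAP Section 8.2.2.1:

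1. No diary entry dated on or before the first-dose date may enter a post-baseline PSSD score.
2. The Week 1 PSSD score is taken from study Days 2 to 8 of the daily diary, with the existing requirement of at least 4 of 7 entries.

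The second sentence is needed because the first alone would leave a Day 5 visit without a score. Overlap with baseline at Week 1 then falls to 0 for every visit date. The visit-anchored windows from Week 2 onwards stay as they are, so no Week 16 key secondary endpoint is re-windowed.

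The cost is SAP wording and programming, with no new data. The small downside is that for some subjects the Week 1 PSSD week ends a few days before or after the Week 1 clinic assessment: 3 days after a Day 5 visit, or 3 days before a Day 11 visit.
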